### 5.2.6 Safety laboratory investigations

Blood samples for safety analysis will be collected at the time points specified in the Flow Chart and analyzed in the investigator's local laboratories. Safety laboratory examinations will include hematology, biochemistry, urine examination and a pregnancy test. In case of neutropenia, blood will be examined as clinically indicated at the discretion of the investigator until recovery.

The following parameters will be determined

**Hematology:**

red blood cell count (RBC), haemoglobin, hematocrit, white blood cell count (WBC) and differential, platelets.

**Biochemistry:**

glucose, sodium, potassium, calcium, creatinine, aspartate, aminotransferase (AST), alanine amino transferase (ALT), alkaline phosphatase, lactate dehydrogenase, bilirubin, urea, total protein, uric acid, creatine phosphokinase (CPK), in case of pathological CPK further evaluation (e.g., by Troponin assays, CK-MM, CKMB, ECG exam) should be performed and the findings documented. GFR will be estimated by the Cockcroft-Gault formula utilizing serum creatinine values (appendix 10.5).

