-  Visit frequency will be as follows: every month for the first 6 months after RT (C1 to C6), every 2 months thereafter for the next six months (C8,C10,C12) and then every three months for the following year (C15,C18,C21, C24), and every 6 months thereafter (C30, C36.....). During the maintenance treatment phase visits should be performed as scheduled wherever possible, but within 2 days of the schedule date.
-  EOT: end of treatment visit; within 5 calendar days after permanent termination of trial drug intake. Investigations to be performed instead of the scheduled visit when a patient discontinues study treatment permanently. If permanent discontinuation of study drug falls on a scheduled visit, examinations as defined for EOT should be performed instead of the examinations of the scheduled visit.
-  FU: Follow-up visit: 28 days ( $\pm 4$ ) after EOT.
-  Early postoperative MRI (within 72 hours after initial surgery) preferable. In case a patient did not perform a Gd-enhanced MRI within 72 hours post surgery, a Gd-MRI is to be performed prior to start of study treatment MRIs should be performed between day 21 and day 28 of Cycle 2, 4, 6, 8, 10 and 12. In the second year, MRIs are performed every 3 months (Cycle 15, 18, 21, 24) and every six months thereafter (Cycle 30, 36...). The EOT MRI/tumour assessments are not required if performed in the previous 4 weeks.
-  For women of childbearing potential only.
-  Same method (Echo or MUGA) must be performed throughout study.
-  Includes height (at screening only) and weight.
-  ECG will be performed at Cycle 2 and every 8 weeks thereafter until cycle 12 (Cycle 4, 6, 8, 10, 12.) and then every three months for the following year (C15, C18, C21, C24), and every 6 months thereafter (C30, C36.....).
-  MMSE will be repeated at Cycle 2, 4, 6, 8,10 ,12 and then every three months for the following year (C15, C18, C21, C24), and every 6 months thereafter (C30, C36.....).
-  Includes CBC, serum biochemistry, and urinalysis, see Section 5.2.6 for details.
-  If not recovered at EOT, or new drug related AE
-  For detailed timing refer to Section 5.5.1 and 10.1
-  RT should be performed between 2 weeks and 6 weeks post surgery

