Diarrhoea is the single most often reported gastrointestinal AE. An increased incidence of diarrhoea grade 3 (22.4%) has been observed in phase II monotherapy trials (starting dose of 50 mg qd). Prompt and proactive management of diarrhoea together with timely treatment pause and dose reduction is crucial to reduce the severity of diarrhoea and its potential complications such as dehydration leading to serum electrolyte changes (hyponatraemia, hypokalaemia and hypomagnesaemia) and/or renal impairment.

Nausea and vomiting are the other commonly reported gastrointestinal adverse events and can be generally managed successfully with the use of antiemetics.

Skin related adverse events present in a number of forms, i.e., rash (including erythematous, maculo-papular, papular, etc.), acne, dermatitis acneiform, dry skin, skin reaction and pruritis. Folliculitis as well as nail changes (including paronychia) are other reported manifestations of skin-related adverse events with BIBW 2992. Early and adequate management of skin-related adverse events can reduce the frequency and the severity of them (R07-4077).

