#### b) Non-hematologic adverse reaction:

1. CTCAEv3 Grade  $\geq 3$  nausea or vomiting is occurring despite appropriate use of standard anti-emetics for at least three days.
2. CTCAEv3 Grade  $\geq 3$  diarrhoea despite appropriate use of standard anti-diarrheal therapy for at least three days.
3. CTCAEv3 Grade  $\geq 3$  rash despite standard medical management as outlined in Section 4.2.3 and lasting  $>7$  days.
4. CTCAEv3 Grade  $\geq 2$  cardiac left ventricular function.
5. CTCAEv3 Grade  $\geq 2$  worsening of renal function as measured by serum creatinine, newly developed proteinuria, or newly developed decrease in glomerular filtration rate.
6. All other non-hematological toxicities of CTCAEv3 Grade  $\geq 3$

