7.8.2 Laboratory data

The analyses of laboratory data will be descriptive in nature and will be based on BI standards. (7)

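### Magnesium is missing from the scheduled safety panel although the protocol names hypomagnesaemia as a complication of diarrhoea, so a possible DLT may be under-ascertained

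*Protocol*

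**What the plan says.** **The named harm.** In Protocol Section 1.2.1, the account of the Phase I and II programme says: "Diarrhoea is the single most often reported gastrointestinal AE". It lists as possible complications "dehydration leading to serum electrolyte changes (hyponatraemia, hypokalaemia and hypomagnesaemia) and/or renal impairment".

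**The panel.** The biochemistry list in Protocol Section 5.2.6 begins "glucose, sodium, potassium, calcium, creatinine" and continues with liver enzymes, LDH, bilirubin, urea, total protein, uric acid and CPK, plus an estimated GFR. Magnesium is not there. The flow-chart footnote on safety labs defers to this list: "Includes CBC, serum biochemistry, and urinalysis, see Section 5.2.6 for details".

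**The DLT definition.** Protocol Section 5.2.3 covers laboratory abnormalities as well as adverse events, provided they are considered related to BIBW 2992. Its last non-haematological item is a catch-all, "All other non-hematological toxicities of CTCAEv3 Grade" 3 or higher, with no exemption for electrolytes. SAP Section 5.1 makes the primary endpoint at least one investigator-defined DLT with onset in the concomitant treatment period.

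**The analysis.** SAP Section 7.8.2 states: "The analyses of laboratory data will be descriptive in nature and will be based on BI standards". It names no analyte.

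**The concern.** The panel covers every biochemical complication of diarrhoea that the protocol itself names, except one. Sodium and potassium are measured, and renal impairment is covered by creatinine and estimated GFR. Magnesium is not measured, and no reason is given.

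This bears on the primary endpoint because a DLT defined by a laboratory value needs that value. Under Protocol Section 5.2.1 a laboratory change is recorded as an AE only when it leads to action with the drug or to treatment, and is not already part of a reported event. An unmeasured change cannot enter by that route. Any resulting error runs one way: unseen events lower the DLT count, which favours escalation and a higher MTD. A low number of hypomagnesaemia AEs could also be taken as reassurance when nobody was required to look.

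**Working it through.** **1. Match the named harms to the panel.**

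| Complication named in Section 1.2.1 | Measured under Section 5.2.6? |
|---|---|
| Hyponatraemia | Yes (sodium) |
| Hypokalaemia | Yes (potassium) |
| Hypomagnesaemia | No |
| Renal impairment | Yes (creatinine, estimated GFR) |

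**2. Look for magnesium elsewhere.** The flow-chart footnotes for both regimens and the visit tables in Protocol Section 6.2 refer back to Section 5.2.6 and add nothing. The liver-injury work-up in Appendix 10.8 does not include it. The diarrhoea guidance in Section 4.2.3 prompts no electrolyte test. The follow-up triggers within Section 5.2.6 are neutropenia, abnormal CPK and abnormal urine findings. The SAP names no other source. In the radiotherapy period there are five scheduled safety-lab visits (Days 1, 8, 15, 29 and 42), and none yields a magnesium result under the plan.

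**3. Ask whether other DLT criteria already catch the patient.** The endpoint is per patient, so a second DLT in the same patient changes nothing. Section 5.2.3 b) already counts Grade 3 or higher diarrhoea that persists despite at least three days of standard therapy (item 2), renal worsening of Grade 2 or higher (item 5), and related low sodium or potassium of Grade 3 or higher (item 6). Not caught by item 2 are prolonged Grade 2 diarrhoea, which Section 4.2.3 nonetheless regards as a reason to pause treatment, and Grade 3 diarrhoea controlled sooner. In those patients hypomagnesaemia could be the only DLT.

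**4. See what one missed DLT does under the rules in Sections 4.1.4.1.1 and 5.2.4.** The plan's own limit is 1 of 6: 1/6 = 16.7%, stated as 17%.

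| Patients | True DLTs | Seen if one is missed | Decision |
|---|---|---|---|
| 3 | 1 | 0 | Changes: escalate instead of expand |
| 3 | 2 | 1 | Changes: expand instead of stop |
| 3 | 3 | 2 | Same: stop |
| 6 | 1 | 0 | Same: dose acceptable |
| 6 | 2 | 1 | Changes: dose acceptable instead of stop |
| 6 | 3 | 2 | Same: stop |

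**5. Illustration only.** The documents give no hypomagnesaemia rate, so the rates here are assumed. Let p be the per-patient DLT probability and q = 1 − p. A dose clears the rule with 0 of 3, or with 1 of 3 followed by 0 of 3: P(clear) = q³ + 3pq⁵. Take 0.167 for all other DLTs and an independent rate m for related hypomagnesaemia of Grade 3 or higher, so that the full rate is p = 1 − (1 − 0.167)(1 − m).

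- Events missed: p = 0.167, P(clear) = 0.833³ + 3 × 0.167 × 0.833⁵ = 0.779.
- m = 2%, counted: p = 0.184, P(clear) = 0.744; difference 0.035.
- m = 5%, counted: p = 0.209, P(clear) = 0.690; difference 0.089.
- m = 10%, counted: p = 0.250, P(clear) = 0.599; difference 0.180.

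Independence ignores the overlap in step 3. If hypomagnesaemia clusters in patients who have another DLT anyway, the differences are smaller.

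**The case against.** The strongest reply is overlap. Section 1.2.1 describes a chain from diarrhoea through dehydration to electrolyte and renal changes, and severe cases along that chain often meet another DLT criterion. Only a related case of Grade 3 or higher, within the radiotherapy period and in a patient with no other DLT, alters the count. That stands and limits the likely effect, but step 3 shows that it does not remove it.

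It is also fair to say that hypomagnesaemia appears in background text, as a potential complication with no frequency, and that the choice of panel is partly the sponsor's judgement. The DLT and MTD definitions are not contradicted.

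Three stronger readings are tempting but not supported.

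- **That the harm cannot be detected.** Adverse events are asked about at every treatment visit, laboratories are local, and nothing bars an unscheduled magnesium test. What is missing is routine measurement.
- **That it will be reported as rare or absent beside fully reported sodium and potassium.** An unmeasured analyte has no row in a laboratory table; it is not shown as zero. SAP Section 7.8.2 defers to a sponsor standard that is not reproduced, so how sodium and potassium will be shown cannot be verified either.
- **That the diarrhoea rate gives the number of missed events.** The protocol reports: "An increased incidence of diarrhoea grade 3 (22.4%) has been observed in phase II monotherapy trials". Applied to the 48 planned patients this gives 48 × 0.224 = 10.8, but that counts patients with diarrhoea, not hypomagnesaemia or missed DLTs. The rate comes from a 50 mg starting dose, whereas escalation here stops at 40 mg.

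Finally, a new analyte cannot recover data from patients already treated. The protocol refers to amendment 5 and to marketed product (Section 6.3), although enrolment status is not stated. For earlier patients only the reporting caveat helps.

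**Conclusion.** The point holds as a modest ascertainment gap that is cheap to close. The protocol names three electrolyte complications and schedules measurement of two. Hypomagnesaemia may therefore be under-ascertained, and a case that qualifies as a DLT could be missed when it causes no symptoms and no site orders the test.

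The direction is known: missed DLTs lower the count. The size is not, because neither the hypomagnesaemia rate nor the overlap with other DLT criteria is given. The differences of 3.5 to 18 percentage points in the working rest on assumed rates of 2% to 10% and on independence; they show sensitivity and are not an estimate. One missed DLT can change the escalation decision in a cohort of 3 to 6, but it need not. Nothing here shows that the MTD would be wrong.

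**What to change.** Reconcile Protocol Section 5.2.6 with Section 1.2.1 by adding serum magnesium to the biochemistry list, run locally on blood already drawn at each safety-lab visit. Include it in the laboratory tables under SAP Section 7.8.2.

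For patients treated before the change, add a sentence to SAP Section 7.8.2 stating that magnesium was not systematically measured, so that a low or zero hypomagnesaemia count is not evidence of absence. This can be done at any time before reporting, even if no amendment is made.

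The cost is a small assay charge, one eCRF laboratory field and a minor amendment, with no extra visit or blood draw. The reported AE or DLT count may rise slightly.

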**Urine examination**

pH, glucose, erythrocytes, leukocytes, protein, nitrite will be analyzed at the time points specified in the protocol. In case of abnormal findings, further evaluation should be performed and the findings documented.

**Pregnancy test**

β-HCG testing in urine or serum will be performed as outlined in the Flow Chart in women of childbearing potential.

**5.2.7 Physical examination, performance score**

A physical examination will be performed at screening and at the time points specified in the Flow Chart. The physical exam serves as a clinical tumour assessment and should include a thorough exam, particularly of the neurological status. Additional symptoms which have not been reported during a previous examination should be clarified. Wherever possible the same investigator should perform this examination throughout the study. Measurement of height (at baseline only) and body weight (in kg) should be included in the physical examination. Evaluation of the Karnofsky performance score (Appendix 10.4) will be performed at the time points specified in the Flow Chart.

**5.2.8 Mini Mental State Examination (MMSE)**

MMSE assessment (appendix 10.4) will be performed at baseline and at the time points specified in the Flow Chart.

**5.2.9 ECG**

A 12-lead resting ECG will be performed at the time points specified in the Flow Chart.

**5.2.10 Left ventricular function**

Left Ventricular Ejection Fraction (LVEF) as measured by echocardiography or MUGA scan will be assessed at time points specified in the Flow Chart. The same method of measurement has to be used throughout the study.

### MUGA Scan

The Multiple Gated Acquisition scan (MUGA) is recommended as a non-invasive method for the assessment of diseases of the heart muscle. It is used for the monitoring of the ejection fraction of the cardiac ventricles, especially the left ventricular ejection fraction (LVEF).

### Echocardiography (ECHO)

Echocardiography should be performed to assess the LVEF according to the standard guidelines of the American Society of Echocardiography (R06-1414).

#### **5.2.11 Vital signs**

Vital signs (blood pressure, pulse and respiratory rate after 2 minutes supine rest) and temperature will be recorded at the screening visit and at the time points specified in the Flow Chart.

### **5.3 OTHER**

#### **5.3.1 Demographics and history**

Demographics (sex, birth date, race), smoking, alcohol history and baseline conditions will be collected during the screening visit. History of malignant brain tumour will be obtained at diagnosis and at the inclusion into the trial and reported in the eCRF:

- the date of first histological diagnosis (month and year may be sufficient)
- the primary tumour location (frontal, parietal, occipital, temporal)

#### **5.3.2 Concomitant therapies and diagnoses**

Concomitant diagnoses and/or therapies present at study entry and/or during screening and relevant to the patient's safety during the trial as judged by the investigator will be recorded in the eCRF.

### **5.4 APPROPRIATENESS OF MEASUREMENTS**

The Macdonald criteria (R08-1053) to be used for evaluation of tumour response are well established and scientifically accepted. The CTCAEv3 criteria (R06-1666) are used in the assessment of adverse events in cancer patients as well as the Karnofsky Performance Scale (Appendix 10.3).

The MMSE assessment (R96-2656) to assess cognitive impairment at a given point in time and to follow the course of cognitive changes in an individual over time is a widespread tool used in neuro-oncology (appendix 10.4).

### **5.5 DRUG CONCENTRATION MEASUREMENTS - PHARMACOKINETICS**

Date and exact clock time of administration as well as of PK plasma sampling times have to be recorded.

### **5.5.1 Methods and timing of sample collection**

- For quantification of BIBW 2992 plasma concentrations 4 ml of venous blood will be collected at the following time points:
- Visit 2 (Day 8): Before (-0:05 h) the administration of BIBW 2992.
- Visit 3 (Day 15): Before (-0:05 h) the administration of BIBW 2992, around 1 hour (within a time frame between 0.5-2.0 hours) and around 3 hours (within a time frame between 2.0 and 4.0 hours) after drug administration. One voluntary PK sample may be taken at any time within the time frame of 4 hours to 24 hours (preferentially 6 hours) after BIBW 2992 administration.
- Visit 4 (Day 29): Before (-0:05 h) the administration of BIBW 2992.

Date and exact clock time of BIBW 2992 administration, as well as blood collection times, must be recorded in the eCRF. Additionally, the date and time of drug intake of the patients for the last four (4) days prior to pharmacokinetic sampling should be documented in the eCRF.

Correct, complete and legible documentation of drug administration and blood sampling times is mandatory to obtain data of adequate quality for the population pharmacokinetic analysis.

The detailed timing of PK sampling is attached to this protocol as Appendix 10.1. The detailed procedures for collecting the samples are attached to the ISF. For storing and shipping conditions of these samples please refer to the ISF.

### **5.5.2 Analytical determinations**

BIBW 2992 drug concentrations will be determined by a validated by a high performance liquid chromatography-mass spectrometry (HPLC-MS/MS) assay. The procedure and specification of the analytical method are available at the determination site (Department of Drug Metabolism and Pharmacokinetics, Boehringer Ingelheim Pharma GmbH and Co. KG, Biberach, Germany).

## **5.6 BIOMARKER - PHARMACODYNAMIC SAMPLING**

### **5.6.1 Methods and timing of sample collection**

#### **5.6.1.1 Tumour samples**

Tumour samples from enrolled patients will be collected as early as possible after informed consent 1 have been obtained. They will need to be sent to a central laboratory for methylation MGMT promotor status determination. Only tumour slices from open surgery are suitable (4 x 10 micron slices).

**Note:** If a patient already has proven MGMT promotor methylation status prior to screening and the test performed by the same laboratory used in the 1200.38 study, the patient will be able to enter in the study without re-testing.

For patients who received trial medication for more than a year:

Archived tumour samples may be collected after informed consent has been obtained. Samples can date back to surgery and/or biopsy. Block or tumour slices (11 x 4 micron slices) are suitable. No new biopsy or surgery will be required for this purpose.

All tumour specimens must be adequately labeled by the Pathology Department providing the specimen for analysis.

Details with regards to tissue collection, labeling and shipping instruction can be found in the ISF at each investigational site.

### **5.6.2 Analytical determinations**

Tumour samples will be analyzed for MGMT methylation status.

For patients who received trial medication for more than a year:

Archived tumour samples may be analysed for acquired mutations in genes associated with cancer, including but not limited to EGFR, EGFRvIII, PTEN, P-AKT, by a centralized third party vendor. In addition, fluorescent in situ hybridization (FISH) analyses could be performed for EGFR and PTEN. As medical knowledge in this field is constantly evolving, additional tissue biomarkers that come to be known as potentially relevant prognostic/predictive markers of treatment response may also be explored. The results of these analyses will be reported.

## **5.7 PHARMACOKINETIC - PHARMACODYNAMIC RELATIONSHIP**

No analysis of PK/PD relationship is planned. However, if the data suggest a PK/PD relationship of special parameters described in 5.6 or correlation of efficacy of safety data to PK, a detailed analysis of PK/PD relationship might be performed.

## **5.8 DATA QUALITY ASSURANCE**

The trial will be conducted in compliance with the protocol, the principles laid down in the Declaration of Helsinki, local law and according to the principles of GCP and the company standard operating procedures (SOPs).

An investigator meeting or conference call will be performed prior to start of the trial to inform all investigators about the trial drug and the procedures of the trial. Alternatively, each investigator could also be visited individually by one of BI's clinical research associates (CRA).

Each investigator will receive an ISF with all information relevant for the performance of the trial. Investigators will be visited intermittently for on-site monitoring by a Boehringer Ingelheim employee or a CRA authorized by BI. On these occasions, source data verification will be performed and a check will be done whether the eCRFs are kept current. The information in the eCRF that has to be documented in source documents will be cross-checked as described in Section 8.2.4.

A quality assurance audit of this study may be conducted by the sponsor or sponsor's designees. The quality assurance auditor will have access to all medical records, the investigator's study related files and correspondence, and the informed consent documentation that is relevant to this clinical study.

The data management procedures to ensure the quality of the data are described in detail in the trial data management and analysis plan (TDMAP) available in the CTMF. Coding of the Adverse events and Concomitant Diagnoses will be done by using the medical dictionary for regulatory activities (MedDRA). Coding of the Concomitant therapies will be done by using the WHO drug dictionary (WHO-DD).

## **6. INVESTIGATIONAL PLAN**

### **6.1 VISIT SCHEDULE**

Patients will visit the investigator at the time points specified in the Flow Chart.

The screening process is divided into two visits, Screening Visit 1 and Screening Visit 2. At Screening Visit 1, tumour sample from open surgery will be analysed by a central laboratory for MGMT gene methylation status.

Patients will be able to proceed to Screening visit 2 if:

- the patient has a proven MGMT promotor methylation status
- the cohort corresponding to the patient MGMT promotor methylation status is not full

The decision to pursue to screening visit 2 will be made after agreement with the Trial Clinical Monitor (TCM)

During the maintenance treatment phase visits should be performed as scheduled wherever possible, but within 2 days of the schedule date.

All patients should be evaluated within 5 calendar days after permanent termination of trial drug intake (EOT visit)

All patients should also have a follow-up visit 28 days (+/- 4days) after the EOT visit.

The clinical trial will be considered completed as soon as the last patient receiving treatment has completed the follow-up assessment 28 days after EOT.

In case the trial will be finished by the sponsor for safety reasons, patients will not continue treatment with the trial drug.

